Study objectives	
Primary objective: Relapse free survival (RFS) of Flt3-ITD+ AML patients in complete hematological remission after allo-SCT receiving Sorafenib maintenance therapy versus placebo
 
Secondary objective:
 
 1. To compare the median overall survival (OS) of Flt3-ITD+AML patients in CHR after allo-SCT receiving Sorafenib maintenance treatment versus placebo 2. To compare the median RFS and OS of Flt3-ITD+ AML patients with and without NPM mutations receiving Sorafenib versus placebo 3. To compare the median RFS and OS of Flt3-ITD+AML patients in CHR after allo-SCT receiving Sorafenib maintenance treatment versus placebo depending on the baseline expression level of Flt3-ITD at diagnosis 4. To compare the toxicity of Sorafenib maintenance versus placebo 5. To longitudinally evaluate biomarkers associated with Sorafenib treatment response and Sorafenib resistance and correlation with RFS and OS 6. To assess safety with type, severity graded by NCI CTC criteria version 4.02.

Primary endpoint	
Relapse free survival (RFS), 50 events (relapse)
 
RFS is defined as time interval from randomization until relapse of AML or death from any cause, which ever occurs first. Relapse is defined as any blast appearance in the peripheral blood, in the bone marrow (> 5%) or extramedullary blasts (chloroma). For a patient with no relapse before the end of study follow-up, observation of RFS will be censored at the date of his or her last follow-up examination.

Secondary endpoint	
Overall survival
 
Overall survival is defined as time from randomization to the day of death. For a patient who is not known to have died by the end of follow-up, observation of OS will be censored on the date the patient was last known to be alive.

Planned number of patients	Total number of patients: 200
Diagnosis	FLT3-ITD positive AML after allo-SCT in CHR
Criteria for inclusion	
 • Written informed consent • Age ≥ 18 y. • ECOG performance ≤ 1 • FLT3-ITD-positive AML • Complete hematological remission (CHR) after allo-SCT CHR must be confirmed by bone marrow analysis within 14 days before randomization (CHR criteria are: $\leq 5\%$ marrow blasts, no peripheral blasts, blood platelet count $> 100/nl$, WBC count $> 3 G/L$, ANC $> 1 G/l$). • Allo-SCT with a HLA-identical allo-family donor (FAM) or a matched unrelated donor (MUD) with up to 1 antigen mismatch acceptable (9/10) • Time point of study treatment start of patients in CHR: between d+60 up to d+100 after allo-SCT • Adequate organ function: Serum creatinine ≤ 1.5 x upper normal value ALT, AST, AP ≤ 2.5 x upper normal value Total bilirubin ≤ 1.5 x upper limit of normal PT-INR/PTT ≤ 1.5 x upper limit of normal • Patients who are being therapeutically anticoagulated with an agent such as Coumadin or Heparin will be allowed to participate in the trial provided that the medical need for anticoagulation is evidence-based (level 1 evidence) and PT-INR and PTT values are closely monitored to maintain the therapeutic window. • Negative serum pregnancy test within seven days prior to first dose in women of child-bearing potential (WOCBP) • WOCBP must use a double barrier method of contraception during the study and for 3 months following the last dose of study drug. WOCBP are defined as sexually mature women who have not undergone a hysterectomy or surgical sterilization or who have not been naturally postmenopausal for at least 12 consecutive months (i.e., who has had menses any time in the preceding 12 consecutive months). • Male subjects whose sexual partners are WOCBP must use a double barrier method of contraception, one of which includes a condom, during the study and for 3 months after the end of treatment.
Criteria for exclusion	
 • Any severe concomitant conditions which make it undesirable for the patient to participate in the study or which could jeopardize compliance with the protocol (such as

[figure not shown]
	
substance abuse, uncontrolled infection, known HIV, HBV, HCV infection
 
 • Psychiatric disorder that interferes with ability to understand the study and give informed consent, and/or impacts study participation or follow-up. • Cardiac disease: heart failure NYHA III/IV, unstable coronary artery disease (MI more than 6 months prior to study entry is permitted), serious cardiac ventricular arrhythmias requiring anti-arrhythmic therapy (beta-blockers or digoxin are permitted) • Resting blood pressure consistently higher than systolic 150 mmHg and/or diastolic 90 mmHg despite antihypertensive therapy • Patients undergoing renal dialysis • Evidence or history of severe non-leukemia associated bleeding diathesis or coagulopathy • Patients with uncontrolled seizure disorder despite medication • History of organ allograft (except for allogenic SCTX) • Patients with major surgery, open biopsy, or significant traumatic injury within 4 weeks prior to start of first dose of study drug • Serious non-healing wound, ulcer or bone fracture • Known Flt3-kinase inhibitor resistance • Previous Sorafenib therapy • Active (uncontrolled) graft versus host disease GvHD (> grade I) at time of randomization despite the use of adequate therapeutic measures • Investigational drug therapy outside of this trial during or within 4 weeks of study entry • Pregnancy or breast feeding • Allergy to study medication or compositions of excipients in study medication • Secondary allo-SCT • Previous or concurrent cancer curatively treated ≤ 3 years prior to study entry

Investigational therapy: dose/mode of administration/ dosing schedule
	
Product: Sorafenib, 200mg / tablet
 
Mode of administration: Oral, tablet
 
Dosing schedule: Dose level 1 (starting dose) : 2 tablets / day (1-0-1) Dose level 2 (escalated dose): 3 tablets / day (1-0-2) Dose level 3 (targeted dose) : 4 tablets / day (2-0-2)
 
 • Dose level 1 will be given for 2 weeks • Dose level 2 applies for 4 weeks • If dose level 2 is well tolerated, the targeted dose will be administered, starting 6 weeks after treatment initiation • Study medication will be administered up to 2 years or until relapse

Reference (comparator) therapy:	Product: matching placebo Mode of administration: Oral, tablet Dosing schedule: Dose level 1 (starting dose) : 2 tablets / day (1-0-1) Dose level 2 (escalated dose): 3 tablets / day (1-0-2) Dose level 3 (targeted dose) : 4 tablets / day (2-0-2) 
 • Dose level 1 will be given for 2 weeks • Dose level 2 applies for 4 weeks • If dose level 2 is well tolerated, the targeted dose will be administered, starting 6 weeks after treatment initiation • Placebo will be administered up to 2 years or until relapse
Tolerability/safety variable(s)	Safety with type, severity graded by NCI CTC criteria version 4.02
Statistical methods	Kaplan-Meier method, log-rank test, Cox regression, intention-to-treat analysis
Sample size calculation and explanation	Assuming a relapse-free survival rate of 65% with placebo and 82.5% with Sorafenib at two years, corresponding to a hazard ratio of 0.45, a total of 200 patients for both study arms (i.e., 100 per arm) is needed to obtain a power of 80% with the log-rank test at a two-sided alpha of 0.05, allowing for a drop-out rate of 8%.

2.1. Flow Chart

2.1.1. Study eligibility criteria at different time points

3. Introduction and study background

3.1. Disease background

Acute myeloid leukemia (AML) is the most frequent acute leukemia of adults and has an unfavourable prognosis [1]. Factors, which come along with a poor prognosis are age over 60 years, poor ECOG performance status prior to therapy, secondary AML, a white cell count of more than 20.000 G/l or an elevated lactate dehydrogenase at presentation [2]. Also certain cytogenetic and molecular aberrations are associated with a poor prognosis, e.g. those with particular mutations in the Flt3-receptor tyrosine kinase (RTK) [3]. Flt3 is a type III RTK regulating the hematopoietic progenitor cell homeostasis. The Flt3-RTK activates several conserved pathways, including the Ras/Map-kinase, the phosphoinositide-3-kinase/Akt signaling cascade and Stat-5 [4] [5,6] [7]. Constitutive activation of these pathways occurs through mutations in Flt3, such as those leading to internal tandem duplications in the juxta-membrane domain of the receptor (Flt3-ITD) [8] [9]. The biological consequences of aberrant Flt3-ITD signaling are transformation, resistance to apoptosis, and prevention of differentiation of leukemic blasts in acute myeloid leukemia (AML) [10] [11]. Flt3-ITD can be found in approximately 20% of AML patients and is associated with a poor risk status [12], [13-15] [3]. Therefore, several specific Flt3-inhibitors have been developed and evaluated in clinical trials (for review see ref. Knapper 2007 [16]). However, their overall clinical efficacy in all cases of AMLs must so far be considered as minor (Knapper 2007). The initial treatment of AML consists of two phases. Complete remissions could be achieved after the induction phase in 50% in patients older than 60 years and 70% to 80% in younger patients. To prevent relapse a second phase (consolidation) is applied either as chemotherapy, autologous or allogeneic stem cell transplantation. Transplantation is more often used in young patients with adverse prognosis as it is true in the case of Flt3-ITD positive AMLs.

3.2. Investigational product background

Sorafenib (Nexavar TM) is a novel RAF, Flt3 and VEGFR kinase inhibitor that prevents tumor growth by combining two anticancer activities: inhibition of tumor cell proliferation and tumor angiogenesis.

Sorafenib was developed as an oral cytostatic Raf kinase inhibitor, PDGFR inhibitor and VEGFR-2 (KDR) inhibitor, for the potential treatment of various cancers. It functions by inhibiting the Raf kinase as constituent of the classical mitogen-activated protein kinase (MAPK) signaling cascade [17]. Raf and other members (such as Ras) of this pathway are attractive targets for development of anti-neoplastic agents because their aberrant activity has been heavily implicated in the onset of a variety of cancers. When properly regulated, the classical MAPK (Raf/MEK/ERK) pathway controls a variety of cellular functions such as proliferation, differentiation, and apoptosis. Genetic mutations can, however, lead to overexpression or aberrant activity of a particular MAPK. Furthermore, it is widely known that MAPK hyperactivity can lead to tumorigenesis.

More recently, it has also been shown that Sorafenib is a strong inhibitor of the receptor tyrosine kinase Flt3 that has been implicated in the pathogenesis of AML (see above) [18]. Also, Sorafenib inhibits the activity of VEGF receptors, which are expressed on the surface of AML blasts as well as on the surface of surrounding bone marrow micro-vessels. Micro-vessel density is greatly increased in AML bone marrow and it is possible that by inhibition of VEGF receptors, leukaemia induced neoangiogenesis is targeted, providing a further rationale for the treatment of AML with Sorafenib.

In summary, Sorafenib targets several tyrosine kinases that have been implicated in the pathogenesis of AML, including the classical MAPK pathway, angiogenic VEGF receptors and the receptor tyrosine kinase Flt3.

3.3. Rationale for the study

Sorafenib has been approved for the treatment of advanced renal cancer and advanced hepatocellular carcinoma [19]. It inhibits the serine threonine kinase Raf-1, but also the Flt3-RTK, and Flt3-ITD [20], suggesting that it may have a role also in AML [18].

The major rationale for studying Sorafenib in AML was derived from its treatment efficacy in Flt3-ITD positive AML: in a phase I clinical trial on 16 patients with AML Sorafenib was recently found to be particularly active in Flt3-ITD positive patients [20]. Sorafenib induced a complete molecular remission in a Flt3-ITD positive patient after allogeneic stem cell transplantation (allo-SCT) [21]. In a cohort of consecutive six Flt3-ITD-positive AML patients single agent Sorafenib led to durable complete molecular remissions in two refractory AML patients post allo-SCT [22]. The efficacy of Sorafenib in refractory / relapsing Flt-3-ITD-positive patients was further supported by a report on additional 13 patients, all of which

showing at least a hematological response to Sorafenib including two complete molecular responders (Metzelder et al, ASH 2009 abstract # 2060).

The poor prognosis of Flt3-ITD positive AMLs mainly results from the high relapse rates rather than induction failure [23,24] [25]. Due to the fact that therapeutic options in relapsing patients after allo-SCT are extremely poor, a selective inhibition of Flt3-ITD positive AML blasts with Sorafenib at the time of complete remission may target residual disease and thus be particularly effective.

Presumably, treatment with Sorafenib in the context of an allo-immune effect (the anti-leukemic graft versus leukemia (GvL) effect) may result in a meaningful synergism leading to a significant improvement of the prognosis of Flt3-ITD AML.

3.4. Risk-benefit assessment

Due to a lack of curative treatment alternatives, the prognosis of relapsed Flt3-ITD positive AML after allo-SCT is usually detrimental. Recent data demonstrated a remarkably high therapeutic efficacy of Sorafenib in refractory and relapsed Flt3-ITD positive AML, suggesting that a pre-emptive therapeutic approach after allo-SCT - as planned in this study – may offer to patients the chance to prevent relapse and thus lead to an increased overall survival. There has been limited experience as to the interference of Sorafenib with GvL / GvHD effects and the toxicity resulting from Sorafenib use in the context of a variety of prophylactic medications routinely taken by transplanted patients after allo-SCT. Casuistic treatment experiences suggest that these adverse events can be managed. However, the overall benefit-risk ratio for patients entering this study seems to be clearly favourable.

4. Outcome measures

Aim of this study is to utilize the Flt3-ITD leukemia specific activity of sorafenib after allo-SCT to prevent relapses in the high risk group of patients with Flt3-ITD positive AML.

Toxicity will be evaluated according to toxicity scale Common Terminology Criteria for Adverse Events v4.02 (CTCAE) at <http://evs.nci.nih.gov/ftp1/CTCAE>

GvHD will be documented using the cGVHD Symptom Tracking Chart on www.asbmt.org (see also Tables 5 and 6 in the appendix)

4.1. Objectives

4.1.1. *Primary objective*

Relapse free survival (RFS) of Flt3-ITD+ AML patients in complete hematological remission after allo-SCT receiving Sorafenib maintenance therapy versus placebo

4.1.2. *Secondary objectives*

- To compare the median overall survival (OS) of Flt3-ITD+AML patients in CHR after allo-SCT receiving Sorafenib maintenance treatment versus placebo
- To compare the median RFS and OS of Flt3-ITD+ AML patients with and without NPM mutations receiving Sorafenib versus placebo
- To compare the median RFS and OS of Flt3-ITD+AML patients in CHR after allo-SCT receiving Sorafenib maintenance treatment versus placebo depending on the baseline expression level of Flt3-ITD at diagnosis
- To compare the toxicity of Sorafenib maintenance versus placebo
- To longitudinally evaluate biomarkers associated with Sorafenib treatment response and Sorafenib resistance and correlation with RFS and OS
- To assess safety with type, severity graded by NCI CTC criteria version 4.02.

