11.2. Power and Sample Size Calculation

The primary endpoint of the study, relapse-free survival (RFS), is defined as the time interval from randomization until relapse or death from any cause, whichever occurs first. For a patient with none of these events before the end of study follow-up, observation of RFS will be censored at the date of his or her last follow-up examination. It is assumed that the RFS rate after 2 years may be increased from 65% with placebo (Gale et al., Blood 2005; Thiede et al., Blood 2006) to 82.5% with sorafenib, corresponding to a hazard ratio (HR) of 0.45. Comparing the sorafenib with the placebo group by a log-rank test at a two-sided alpha of 5%, 49 observed events are required to obtain a power of 80%. It is important to note that due to a decreasing likelihood of relapses over time, the Kaplan-Meier curve for RFS of Flt3-ITD AML patients after allo-SCT forms a plateau after around 2 years at the above-mentioned values.

Under these assumptions, 184 patients (i.e., 92 per group) are needed in order to observe 49 events after a minimum observation period of 24 months for each patient. The inclusion of a total of 200 patients in the study allows for compensation of a dropout rate of 8%. During the course of the study, it may be decided to adapt the number of included patients. If this is done based on a data inspection (rather than solely on the absolute number of events which occurred so far, irrespective of the study arm), the method for sample-size adaptation in survival trials developed by Schäfer and Müller (Schäfer H, Müller H-H. Modification of the sample size and the schedule of interim analyses in survival trials based on data inspections. Statist Med 2001;20:3741-3751) will be employed which ensures that the type I error risk is not affected. It may also be decided later to add one or more interim analyses using the adaptive method mentioned above, especially if the sample size is increased.

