observation of OS will be censored on the date the patient was last known to be alive. This and other secondary objectives will be analyzed by the Kaplan-Meier method and the log-rank test. Furthermore, RFS and OS will be analyzed by Cox regression in order to account for prognostic factors (Flt3-ITD ratio at diagnosis, treatment with Flt3-inhibitors before allogenic stem cell transplantation, occurrence of chronic GvH). The analysis will be performed according to the intention-to-treat principle.

With regard to safety, numbers of adverse events will be analyzed descriptively as well as in comparison between the two study arms by means of Fisher's exact test.

12. Efficacy

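### Secondary objectives 1 to 3 compare medians that the design assumptions put out of reach, and the stated methods do not test effect modification

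*Protocol*

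**What the plan says.** Section 4.1.2, repeated in the Synopsis, states the first secondary objective as "To compare the median overall survival (OS) of Flt3-ITD+AML patients in CHR after allo-SCT" on sorafenib versus placebo. The second asks for median RFS and OS in patients with and without NPM mutations. The third asks for the same comparison as a function of Flt3-ITD expression at diagnosis.

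Section 11.2 assumes two-year RFS of 65% with placebo and 82.5% with sorafenib. It adds that the RFS curve of such patients "forms a plateau after around 2 years at the above-mentioned values". Section 4.2.1 counts relapse or death from any cause as an RFS event. Section 7.1.4 ends scheduled contact at month 42.

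For OS and the rest, section 11.4 says: "This and other secondary objectives will be analyzed by the Kaplan-Meier method and the log-rank test". It adds a Cox regression of RFS and OS to account for prognostic factors. The Flt3-ITD ratio is on that list and NPM status is not, and no treatment-by-factor interaction is stated. For safety, "numbers of adverse events will be analyzed descriptively as well as in comparison between the two study arms" by Fisher's exact test. Section 11.3 uses nearly the same words for the interim safety analysis.

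**The concern.** A median exists only if the survival curve falls to 50%. Objectives 1 to 3 name the median as the quantity to compare, while the sample size rests on curves that stay above 50% in both arms. If the trial behaves as planned, the named quantity cannot be reported. An analysis plan that reports hazard ratios instead would depart from the stated objective.

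The third objective asks how the effect depends on a baseline level, and the second may be asking the same about NPM status. Kaplan-Meier curves and log-rank tests within strata give one result per stratum. They do not test whether the strata differ, and a continuous ratio would first have to be cut into groups. The Cox model as described adjusts for the ratio but does not let the treatment effect vary with it. What is at stake is that one significant and one non-significant subgroup is taken as a real difference in effect.

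**Working it through.** **Inputs.** Two-year RFS 65% and 82.5%, hazard ratio 0.45, two-sided alpha 5%, power 80%, 49 events, 184 patients (92 per group), 8% dropout (section 11.2); 1:1 allocation (section 5.5); contact to month 42 (section 7.1.4).

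**The plan's own figures.**
- Hazard ratio: ln 0.825 / ln 0.65 = 0.4466.
- Schoenfeld events: 4 × (1.960 + 0.842)² / (ln 0.4466)² = 48.3, rounded up to 49. This agrees with "by a log-rank test at a two-sided alpha of 5%, 49 observed events are required to obtain a power of 80"%.
- Expected events: 92 × 0.35 + 92 × 0.175 = 48.3, close to 49.
- Total: 184 / 0.92 = 200.

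The design figures reproduce, so the curves used below are those behind the sample size.

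**Medians with the plateau.** Both curves level off above 50%, so neither arm has a median RFS. No patient dies before his or her RFS event time, so each OS curve lies at or above its RFS curve and has no median either. Sampling variation hardly changes this. The binomial chance that at least 46 of 92 patients have an event is 0.2% at an event rate of 35%, and about 1 in 10¹² at 17.5%.

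**Medians without the plateau (exponential).** Median = 24 × ln 2 / (−ln S₂₄).
- Placebo: 24 × 0.6931 / 0.4308 = 38.6 months; RFS at month 42 is 0.65^(42/24) = 47%.
- Sorafenib: 24 × 0.6931 / 0.1924 = 86.5 months; RFS at month 42 is 0.825^(42/24) = 71%.

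The placebo median could then be seen late in follow-up. The sorafenib median could not, so the contrast still cannot be estimated.

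**An alternative that can be estimated.** The design difference in 24-month RFS is 17.5 percentage points. With 92 per arm followed to 24 months, its standard error is √(0.65 × 0.35/92 + 0.825 × 0.175/92) = 6.4 points.

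**Separate subgroup tests.** Take a true hazard ratio of 0.45 in both subgroups and 49 events. Power with d events = Φ(0.7985 × √d / 2 − 1.96), where 0.7985 = −ln 0.45. The protocol gives no subgroup shares, so the splits are assumptions.

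| Split of events | Power in each subgroup | Exactly one significant |
|---|---|---|
| 50:50 (24.5 and 24.5) | 51% and 51% | 2 × 0.506 × 0.494 = 50% |
| 30:70 (14.7 and 34.3) | 33% and 65% | 0.334 × 0.353 + 0.647 × 0.666 = 55% |

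No effect modification is present in either row.

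**Interaction test.** For a true ratio of hazard ratios of 0.45, power = Φ(0.7985 / √(4/d₁ + 4/d₂) − 1.96). This gives 29% at 50:50 and 20% at 20:80.

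**Fisher's test.** If it were applied to event counts, repeated events within a patient would inflate the type I error. A simulation assumed 100 patients per arm, a mean of 3 to 10 events per patient, 30% of events in the category tested, and within-patient correlation of 0.02 to 0.20. The error was about 6% to 35% instead of 5%. If patients with at least one event are counted, the test is valid.

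**The case against.** A reader might infer that the secondary objectives cannot be answered at all. The documents do not support that. Kaplan-Meier, log-rank and Cox analyses need no median, the endpoint definitions mention none, and the planned Cox model already yields a hazard ratio. Sections 4.1.2 and 11.2 still disagree about what can be estimated.

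A reader might also infer that every median will be unreached. The plateau is a planning assumption for whole arms. Section 5.1 admits chemotherapy-refractory disease and second remission, so a poor-prognosis subgroup could fall below 50%, and the protocol gives no subgroup rates.

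On subgroups, the second objective can be read as asking for sorafenib versus placebo within each NPM group, which stratum-wise log-rank tests answer. The Flt3-ITD ratio does enter a Cox model, where no cut-point is stated. Interaction terms are often left to the SAP, which is not at hand, and that weakens this part. What stands is that the protocol names a method for the third objective, and that method does not match the question.

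On safety, it is tempting to say that Fisher's test treats correlated events as independent patients. The wording does not establish this. The safety set is defined by patients, and the usual table for Fisher's test counts patients with and without an event. Only the wording needs repair.

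**Conclusion.** The point holds as a minor one. Under the design assumptions no whole-arm median RFS or OS exists. If the plateau is dropped for an exponential curve, the sorafenib median still lies about 44 months past the last contact (86.5 − 42). So the contrast of medians named in objectives 1 to 3 is not estimable for whole arms, while the comparison of survival itself remains possible.

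For the third objective, and for the second if it concerns effect modification, the methods as described give only within-stratum comparisons or adjusted main effects. The 50% to 55% discordance illustrates the risk of reading those comparisons side by side. It rests on assumed splits, 49 events and a common hazard ratio of 0.45. The primary analysis, the sample size and control of the type I error are untouched.

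**What to change.** - **Section 4.1.2 and Synopsis:** replace the comparison of medians by the hazard ratio with 95% confidence interval and the difference in 24-month Kaplan-Meier rates. Medians can still be shown descriptively where they are reached.
- **Section 11.4:** test treatment-by-NPM and treatment-by-log(Flt3-ITD ratio) interactions in the Cox model, keeping the ratio continuous. Show subgroup hazard ratios with confidence intervals and label all of this exploratory. State whether the second objective asks about effects within NPM groups or a difference between them.
- **Sections 11.3 and 11.4, wording only:** say that Fisher's exact test compares numbers of patients with at least one event.

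The cost is a few lines of text and a little programming. No further patients are needed, and no data beyond those the objectives already require. The downside is low interaction power, about 20% to 29% for a ratio of hazard ratios of 0.45 with 49 events, and less if the interim inspection reduces the event target. The protocol should say so, because a non-significant interaction would not show that the effect is uniform.
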